A Preliminary Study of Prophylactic Fentanyl Pectin Nasal Spray (FPNS) for Exercise-Induced Breakthrough Dyspnea

Principal investigator: [name]

Supportive Care Co-investigators: [name], [name], [name]

Biostatistics Co-investigator: [name]

Table of Contents

| | |
|---|----|
| A. Study Objectives | 2 |
| B. Background | 2 |
| C. Experimental Approach | 5 |
| D. Statistical Analysis | 11 |
| E. Data Confidentiality Procedures | 11 |
| F. References | 11 |

A. Study Objectives

Primary objective

To determine the effect of prophylactic fentanyl pectin nasal spray (FPNS) on the **intensity of exercise-induced breakthrough dyspnea** (numeric rating scale, adjusted for distance walked) between the **first** and **second** 6 minute walk tests. We aim to determine the effect size for both FPNS and placebo arm to inform a larger, adequately powered confirmatory randomized controlled trial.

Secondary objectives

1. To determine the effect of prophylactic FPNS on the **walk distance, neurocognitive function, and adverse effects** between the **first** and **second** 6 minute walk tests.
2. To determine the effect of prophylactic FPNS on the **intensity of dyspnea, walk distance, neurocognitive function, and adverse effects** between the **first** and **third** 6 minute walk tests.
3. To compare prophylactic FPNS and placebo on their ability to reduce the intensity of **exercise-induced breakthrough dyspnea, walk distance, neurocognitive function, and adverse effects** between the **first** and **second** 6 minute walk tests, and also between the **first** and **third** 6 minute walk tests.

B. Background

B.1. Significance of Dyspnea. Dyspnea is a subjective awareness of difficulty breathing, which may be associated with the distressing sensation of suffocation. It is one of the most common and most feared symptoms among cancer patients, occurring in up to 70% of patients in the last 6 weeks of life (Ben-Aharon et al. 2008). Dyspnea is associated with fatigue, anxiety, decreased function and quality of life, and increased mortality (Hauser et al. 2006, Maltoni et al. 2005).

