Based on clinical practice and similarly to the dose used for breakthrough pain, we will use an FPNS dose equivalent to 15-25% of the MEDD (Table 3). For patients randomized to receive FPNS, the study medication will be provided by Dispensing Pharmacy and will then be administered intranasally 20 minutes before the second 6-minute walk test. The same dose will be repeated at least 30 minutes after the first dose and 20 minutes prior to the third and final 6 minute walk test. We estimated the FPNS dose based on the following assumptions:

- A rescue dose of 15-25% of the MEDD is safe and adequate for relief of dyspnea (Bruera *et al.* 1993, Charles *et al.* 2008).
- FPNS has approximately 80% oral bioavailability (Fisher *et al.* 2010, Fisher *et al.* 2010).
- With repeat dosing 30 minutes apart, the maximum concentration (C_{max}) for FPNS is approximately 1.6x higher than the first dose.

The modeled pharmacokinetic data for repeated dosing 30 minutes apart is shown in Figure 2. As a precautionary measure, patients will be asked to wait for 1 hour after completing the last walk before leaving MD Anderson. At the end of 1 hour, they will be assessed by our research staff before being released. If excessive drowsiness or adverse events occur, the study physician will assess the patients.

[figure not shown]

Figure 2. Modeled Pharmacokinetic Data on Repeat Dosing of Fentanyl Pectin Nasal Spray after 30 m

Table 3. Dose of Fentanyl Pectin Nasal Spray Based on Morphine Equivalent Daily Dose^a

| Morphine equivalent daily dose (mg) | Total Fentanyl Pectin Nasal Spray Dose (mcg) | Number of FPNS sprays | Number of Placebo sprays |
|-------------------------------------|--|-----------------------|--------------------------|
| | | | |

| | | | |
|---------|-----|--|---|
| 80-159 | 100 | 1 (100 mcg in one nostril) | 1 |
| 160-239 | 200 | 2 (100 mcg in each nostril) | 2 |
| 240-319 | 300 | 3 (100 mcg in one nostril and 2 x 100 mcg in the other nostril) ^b | 3 |
| 320-540 | 400 | 4 (2 x 100 mcg in each nostril) | 4 |

^aFPNS is available in 100 mcg.

^b For the 300 mcg dose, patients will receive 1 spray in each nostril, then another spray again in the one of the nostrils.

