C.10. Variable rest period. After the first and second 6 minute walk test, patients will be asked to sit down and rest. How long they rest would depend on when they return to baseline level of dyspnea numeric rating score + 1 or below (e.g. if baseline dyspnea = 4, they need to return to a level of 5 or less to qualify for next stage). During this rest period, patients will be assessed every 5 minutes to check their dyspnea level. If their dyspnea level met criteria and they feel ready to walk again, they will be given the study treatment and asked to wait for 20 minutes before they walk. At least 30 minutes should elapse between each dose of the study medication.

C.11. Stopping rules. Patients who do not develop any increase from their baseline dyspnea after the first 6-minute walk will not proceed to the next stage because of the lack of exercise induced dyspnea. If at any time during the study patients develop chest pain, severe leg cramps, staggering, diaphoresis, and/or dizziness, they will be asked to stop the study. If patients require more than 1 hour of rest and their dyspnea level still has not returned to baseline, they will also be taken off study. We plan to replace these patients and any other individuals who are not evaluable because they have not started the 2nd walk test.

C.12. Study assessments. See Table 4 for a detailed description of all study assessments.

Table 4. Summary of Study Assessments

| Assessments | Base-line | Post 1 st 6MWT | Rest #1 | Pre 2 nd 6MW | Post 2 nd 6MW | Rest #2 | Pre 3 rd 6MW | Post 3 rd 6MW |
|--|-----------|------------------------------|---------|----------------------------|-----------------------------|---------|----------------------------|-----------------------------|
| Demographics and cancer diagnosis ¹ | ✓ | | | | | | | |
| Medication history ² | ✓ | | | | | | | |
| Karnofsky performance status ³ | ✓ | | | | | | | |
| Edmonton Symptom Assessment Scale ⁴ | ✓ | | | | | | | |
| Dyspnea Survey ⁵ | ✓ | | | | | | | |
| Cancer Dyspnea Scale ⁶ | ✓ | | | | | | | |
| O ₂ saturation and respiratory rate | ✓ | ✓ | | ✓ | ✓ | | ✓ | ✓ |
| Dyspnea Numeric Rating Scale ⁷ | ✓ | ✓ | ✓ | ✓ | ✓ | ✓ | ✓ | ✓ |
| Dyspnea Borg scale ⁸ | ✓ | ✓ | ✓ | ✓ | ✓ | ✓ | ✓ | ✓ |
| Walking test parameters ⁹ | | ✓ | | | ✓ | | | ✓ |
| Adverse effects ¹⁰ | | | | ✓ | ✓ | | ✓ | ✓ |
| Neurocognitive testing ¹¹ | | ✓ | | | ✓ | | | ✓ |
| Global assessment ¹² | | | | | ✓ | | | ✓ |
| Blinding ¹³ | | | | | | | | ✓ |

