¹⁰ adverse effects related to the use of FPNS, such as dizziness, drowsiness, nausea, stuffy/blocked nose, runny nose, itching/sneezing, nose dryness, cough, sore throat, and taste disturbance will be assessed using a numeric rating scale from 0-10.

¹¹ patients will be asked to do finger tapping 10 and 30 sec, arithmetic, reverse memory of digits, and visual memory). This has been used in other studies by our group.(Bruera *et al.* 1992)

¹² patients will be asked about their dyspnea (worse, about the same, or better) comparing between the level of dyspnea between the first and second 6-minute walk tests (Guyatt *et al.* 1993, Redelmeier *et al.* 1996).

¹³ blinding will be done by asking patients which group assignment they received: "FPNS", "placebo", or "do not know".

¹⁴ study satisfaction is assessed with the following questions, "Was it worthwhile for you to participate in this research study?", "If you had to do it over, would you participate in this research study again?", "Would you recommend participating in this research study to others?", "Did you quality of life get better by participating in this research study?", "Did you quality of life get worse by participating in this research study?"

C.13. Feasibility data. In addition to clinical outcomes, we will also collect feasibility data in this study Rates of recruitment and retention (% of subjects able to complete the study)

- Reasons for refusal and dropout
- Outcome measure—we will compare the sensitivity of Numeric rating scale and Borg scale to change, and identify key measure for future study
- Participant satisfaction—participants will provide an opinion regarding their satisfaction with study overall

C.14. Patient Safety, Monitoring, and Confidentiality. During the study, trained research staff will be performing study assessments and monitoring the patients carefully throughout the study period. A study physician will also be available by pager to address any concerns, distress or questions, and will attend to the patient as needed. Patients will be doing the test in a hallway outside the Supportive Care Center which typically does not have a lot of traffic, and will have immediate access to medical and nursing care if needed. See stopping rules below for further details. With the planned

doses of fentanyl in opioid-tolerant patients, we do not expect any significant side effects.

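### C.11 stops patients for dizziness, itself a scored FPNS effect, but Table 4 schedules no adverse-effect or neurocognitive assessment at an early stop

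*Combined protocol and SAP*

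**What the plan says.** C.11 applies at any time during the study. Patients who develop chest pain, severe leg cramps, "staggering, diaphoresis, and/or dizziness, they will be asked to stop the study". Leg cramps must be severe; dizziness carries no such qualifier. C.11 also plans to replace stopped patients and others who have not started walk 2.

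Footnote 10 to Table 4 defines an outcome made up of "adverse effects related to the use of FPNS, such as dizziness, drowsiness, nausea" and several nasal and throat symptoms, which "will be assessed using a numeric rating scale from 0-10".

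In Table 4, which C.12 presents as the detailed account of all assessments, the row "Adverse effects ¹⁰" is ticked before and after walk 2 and before and after walk 3. The row "Neurocognitive testing ¹¹" is ticked after walks 1, 2 and 3. No column covers a patient who stops early.

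Secondary objective 1 is "To determine the effect of prophylactic FPNS on the walk distance, neurocognitive function, and adverse effects between the first and second 6 minute walk tests". Objective 2 asks for the same from the first to the third walk, and objective 3 compares the arms. D.2 states no rule for missing scores.

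**The concern.** Dizziness is both an outcome to be scored and a reason to end participation, and the assessment schedule is tied to walks that a stopped patient will not do. C.7 gives each dose 20 minutes before a walk, and B.3 puts the time to maximal effect at 15-20 minutes, so drug-related dizziness could well appear during the wait.

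If FPNS causes dizziness, more patients would be stopped in that arm, and those who remain for the later assessments would be the better-tolerating ones. The study exists to inform a confirmatory trial. At stake is whether its tolerability and cognition results, particularly after the second dose, give a fair picture. C.7 expects a maximum concentration about 1.6 times higher with the repeat dose, so the walk-3 assessments are the ones made at the highest exposure.

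**Working it through.** **Step 1: what the schedule yields, by time of stop.** The tick marks come from Table 4 and the stop from C.11. I assume that the pre-walk rating is made towards the end of the 20-minute wait; Table 4 does not fix the minute.

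| Time of stop | Scheduled adverse-effect scores | Scheduled post-dose neurocognitive tests |
|---|---|---|
| After dose 1, before the pre-walk-2 rating | none | none |
| After the pre-walk-2 rating, before walk 2 | pre 2nd | none |
| During walk 2 | pre 2nd; post 2nd only if the stop counts as the end of the walk | post 2nd, on the same condition |
| Rest #2, or after dose 2 but before the pre-walk-3 rating | pre 2nd, post 2nd | post 2nd |
| After the pre-walk-3 rating, before walk 3 | pre 2nd, post 2nd, pre 3rd | post 2nd |

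Two losses are firm under the schedule: the post-dose cognitive test for anyone stopped before walk 2, and all post-walk-3 results for anyone stopped before walk 3. Loss of every post-dose adverse-effect score is confined to the first row.

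**Step 2: how likely a stop is.** The documents give no stopping rate, so I assume p = 5%, 10%, 20% or 30%. D.1 gives 10 evaluable FPNS patients; I use 10 dosed patients for illustration. P(at least one stop) = 1 − (1 − p)^10, which gives 40%, 65%, 89% and 97%. For at least two stops, the binomial tail gives 9%, 26%, 62% and 85%.

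**Step 3: an outer limit on bias.** Suppose the stopped patients were exactly the worst fraction p on a normally distributed score and were not rated at the affected time point. The observed mean would be too favourable by φ(z)/(1 − p) standard deviations, where z is the upper p point: 0.11, 0.19, 0.35 and 0.50 SD for the four rates. The real bias should be smaller, because dizziness does not perfectly order patients on the other scores. With a correlation of 0.5 between dizziness and a cognitive score, under bivariate normality, each figure halves.

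**Step 4: precision.** The plan's only related figure is the 80% power in D.1 (two-sided paired t-test, n = 10, effect size 1.0, alpha 5%). With 9 degrees of freedom and noncentrality 1.0 × √10 = 3.16, exact power is 0.803, so the figure reproduces. For a first-to-third paired contrast with the same standardised effect, 9, 8 or 7 patients give power 0.75, 0.68 or 0.60.

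**The case against.** No section says that a stopped patient is never rated again; the plan is silent. A reader might infer that such patients get no further ratings, but staff could rate them at the stop, and most stop times already leave at least one post-dose adverse-effect score. A patient who reports dizziness at the pre-walk-2 rating has just been scored, and one stopped in Rest #2 has two scores. Footnotes 7 and 8 accept an end-of-walk dyspnea rating when a walk is cut short, so a post-walk assessment after a shortened walk is plausible.

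A reader might also infer that sedation scores are removed. Drowsiness and nausea are not C.11 triggers. C.7 handles excessive drowsiness separately: "If excessive drowsiness or adverse events occur, the study physician will assess the patients". The C.11 list also fits exertional intolerance, which need not differ by arm. Finally, C.7 has staff assess patients 1 hour after the last walk, and C.13 collects reasons for dropout.

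All of this narrows the point. It does not close the gap. The physician and 1-hour assessments name no instrument and are not Table 4 ratings, and dropout reasons carry no 0-10 score or cognitive result. Silence leaves a foreseeable, outcome-dependent stop to staff discretion.

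**Conclusion.** The gap is real but limited. Followed as written, the schedule omits the post-dose neurocognitive test for patients stopped before walk 2 and post-walk-3 results for patients stopped before walk 3. Nothing says that dosed patients who are then replaced stay in the adverse-effect and cognitive summaries. The cognitive summaries and first-to-third contrasts could therefore look too favourable for FPNS, provided that the drug causes dizziness and no unscheduled assessment is made. Walk-2 adverse-effect scores are less affected.

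The size cannot be fixed from the documents. At assumed stopping rates of 5-30%, at least one FPNS patient in 10 is stopped with probability 40-97%, and the outer limit of the bias is 0.11-0.50 SD. The documents do not establish that stopped patients are the most affected on every outcome, or that the highest adverse-effect scores are systematically lost. The outcomes concerned are secondary and the remedy is cheap, so the change is worth making. No view is taken on the stopping rule itself.

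**What to change.** Leave the stopping rule unchanged and make two additions.

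- **C.11 and Table 4:** add an 'at early stop' column and a sentence stating that any patient stopped after receiving a dose completes the footnote 10 ratings at that time, and the neurocognitive tests if able.
- **D.2:** for every patient who received a dose, including those later replaced, report by arm the worst post-dose score for each symptom and the number of C.11 stops with the reason.

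The cost is one sentence, one table column and a short reporting statement, plus a few minutes of existing staff time for each stopped patient. Some neurocognitive tests will be incomplete in patients who are unwell; these should be reported as incomplete, not left out of the count.

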| Patient satisfaction ¹⁴ | | | | | | | | ✓ |

¹ patient initials, medical record number, date of birth, sex, race, education, marital status, cancer diagnosis, co-morbidities, cause(s) of dyspnea.

² medications that could be used to treat dyspnea, including scheduled and as needed opioids, bronchodilators, and steroids will be documented.

³ an 11-point assessment scale that rates patients' functional status between 0% (death) and 100% (completely asymptomatic) based on their ambulation, activity level, and disease severity (Schag *et al.* 1984).

⁴ validated questionnaire that measures 10 common symptoms in the past 4 hours (pain, fatigue, nausea, depression, anxiety, drowsiness, shortness of breath, appetite, sleep, and feeling of well being) using numeric rating scales (Bruera *et al.* 1991).

⁵ characterization of patients dyspnea including the following: presence of dyspnea at rest, average dyspnea in last 24 hours, worse dyspnea in last 24 hours, best dyspnea in last 24 hours, number of episodes of exacerbation per day, triggers of breakthrough dyspnea, average duration of each episode, current treatment for breakthrough dyspnea.

⁶ validated 12-item questionnaire specifically designed to assess the quality of dyspnea in cancer patients during the past few days (Tanaka *et al.* 2000). Each item has a score between 1 and 5, for a maximum of 60. There are sub-scores for sense of effort, anxiety, and discomfort.

⁷ a 0 (no dyspnea) to 10 (worst dyspnea) categorical scale validated for rating the severity of dyspnea (Dorman *et al.* 2007, Gift and Narsavage 1998, Powers and Bennett 1999). We will be measuring it every minute during the 6 minute walk test at 0, 1 min, 2 min, 3 min, 4 min, 5 min and 6 min (or end of walk).

⁸ a 0 to 10 categorical scale for rating the severity of dyspnea. It is a ratio scale with descriptive anchors throughout the range in which a rating of 8 signifies breathlessness twice as severe as 4, which in turn is twice as severe as 2 (Dorman *et al.* 2007, Gift and Narsavage 1998, Kendrick *et al.* 2000, Powers and Bennett 1999). We will be measuring it 0 and 6 min (or end of walk) of each walk. The NRS will be administered before modified Borg scale.

⁹ include the total distance walked, total walking time, the distance and time of first rest due to dyspnea, average walking speed.

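### Satisfaction and the blinding guess are scheduled only after walk 3, with no collection at early exit, so these two results will describe only patients who reach that assessment

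*Combined protocol and SAP*

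**What the plan says.** C.13 lists four kinds of feasibility data: recruitment and retention, why patients refuse or drop out, how sensitive the NRS and Borg scales are to change, and satisfaction. On the last it says that "participants will provide an opinion regarding their satisfaction with study overall". It does not limit this to completers.

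Table 4 (C.12) sets the timing. The row "Patient satisfaction" has a single tick, under Post 3rd 6MW. Footnote 14 gives its five questions, including whether taking part was worthwhile and whether quality of life became worse. The blinding row has the same single tick; footnote 13 says that "blinding will be done by asking patients which group assignment they received", with FPNS, placebo or do not know as the answers. No section schedules either item at another time.

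C.11 provides exits before that point:

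- "Patients who do not develop any increase from their baseline dyspnea after the first 6-minute walk will not proceed to the next stage".
- Any of five listed symptoms, dizziness among them, ends participation whenever it occurs.
- Of patients who rest for more than 1 hour without recovering, it says "they will also be taken off study".

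Patients who have not begun walk 2 are to be replaced. D.1 makes a patient evaluable for the primary endpoint once walk 2 has begun; walk 3 is not required.

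**The concern.** The two items are tied to the last assessment of the visit, while the plan's analysis population is fixed much earlier. A patient can be in the primary analysis of a self-rated outcome, in a trial that C.1 describes as double blind, without having been asked which treatment they think they received. A patient who stops because of symptoms is not asked whether taking part was worthwhile, although that patient's view of burden is of interest when a larger trial is planned.

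Whether an answer is missing may also depend on what the answer would have been. Dizziness is a stopping reason in C.11 and a listed FPNS-related effect in Table 4, footnote 10. Exits after dosing could therefore differ by arm, and they could involve patients with a bodily cue to their assignment.

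**Working it through.** **1. The plan's own figure.** D.1 gives 10 evaluable fentanyl-arm patients, effect size 1.0, two-sided alpha 5%, paired t-test, 80% power. With df = 10 − 1 = 9 and noncentrality 1.0 × √10 = 3.162, the exact noncentral t power is 80.3%, which reproduces the stated 80%. The point does not rest on this figure; it supplies N = 10 for step 3.

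**2. Exits set against the schedule.** Each C.11 exit is compared with doses received (C.1, C.10), evaluability (D.1) and Table 4.

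| Exit | Doses taken | Evaluable? | Satisfaction scheduled? | Guess scheduled? |
|---|---|---|---|---|
| No rise in dyspnea after walk 1 | 0 | No | No | Not applicable |
| Symptoms in walk 1 or rest 1, or rest 1 over 1 hour | 0 | No | No | Not applicable |
| Symptoms in the 20-minute wait after dose 1 | 1 | No | No | No |
| Symptoms in walk 2 or rest 2, or rest 2 over 1 hour | 1 | Yes | No | No |
| Symptoms in the 20-minute wait after dose 2 | 2 | Yes | No | No |
| Symptoms during walk 3 | 2 | Yes | Unclear | Unclear |

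The last row is unclear because footnotes 7 and 8 allow a walk to end before 6 minutes, so a shortened walk 3 may still be followed by its post-walk assessments. The guess has no meaning for patients who were never dosed. That leaves three kinds of dosed exit with no guess, two of them among evaluable patients. Satisfaction is not scheduled for any exit before walk 3.

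**3. Size, without assuming what the missing answers would be.** Let N be the evaluable patients in the arm, k those who leave after walk 2 has begun without being asked, and y the number of positive answers among the N − k who are asked. The proportion among all N lies between y/N and (y + k)/N, so the width is k/N. With N = 10, each patient not asked adds 1/10 = 10 percentage points. If every patient who is asked answers yes (y = 10 − k), the reported rate is 100% and the possible range is:

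| k (assumed) | Lower bound (10 − k)/10 | Upper bound |
|---|---|---|
| 1 | 90% | 100% |
| 2 | 80% | 100% |
| 3 | 70% | 100% |
| 4 | 60% | 100% |

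The documents give no dropout rate (C.3 expects only that most patients will finish), so k is an assumption. D.1 gives no placebo-arm number. If that arm also had 10 evaluable patients, pooled bounds would widen by 1/20 = 5 points per patient not asked.

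**The case against.** The case against giving this much weight is substantial.

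- A reader might infer that the feasibility results as a whole describe completers only. They do not. Retention and reasons for dropout are about non-completers by definition, and Table 4 ticks the NRS and Borg scales at every time point. Of the four C.13 items, only satisfaction is affected. The dropout reasons will also capture part of the burden felt by early exits.
- A reader might infer that early exits cannot be scored. The plan does not schedule the questions at exit, but nothing in it prevents staff from asking them during a single visit.
- A reader might infer that satisfaction will be overstated and blinding made to look better than it was. The documents do not establish either direction. Patients with no rise in dyspnea leave undosed after one walk and need not be dissatisfied. Stop symptoms can come from exertion in either arm, and a placebo patient who stops and guesses FPNS has guessed wrongly.
- A reader might attach a bias to this. For example, 90% positive among completers and 50% among early exits, with 20% leaving early, gives 0.8 × 90% + 0.2 × 50% = 82% against a reported 90%. All three inputs are invented. At this sample size the 8-point gap is less than one patient in 10, and an exact 95% interval around 9 of 10 runs from about 55% to 99.7%.
- Neither item is a primary or secondary objective, neither has a decision threshold, and D.2 gives them only general descriptive statistics. Asking about the study overall at its end is a reasonable default.

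All of this stands as a limit on scope and priority. It does not remove the scheduling gap: C.13 speaks of participants, and a plan followed to the letter will not ask some of them.

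**Conclusion.** The point holds for two results only. As scheduled, satisfaction and the blinding guess will describe patients who reach the post-walk-3 assessment, although evaluability requires only that walk 2 has begun. The missing answers may be informative; their direction and the size of any bias are unknown. What can be stated is the uncertainty: 10 percentage points of best/worst-case width per evaluable fentanyl-arm patient not asked, given D.1's 10 patients and an exit count that the documents do not supply. The primary analysis, sample size and power are unaffected. Priority is minor, and the case for acting is that the change is cheap.

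**What to change.** In Table 4, change the timing of the satisfaction items (footnote 14) to *Post 3rd 6MW or at exit from study*, for all enrolled patients. Give the blinding guess (footnote 13) the same timing for every patient who received at least one dose. Add to D.2 that both are reported by arm with denominators, separating completers from early exits. A finer split by exit point would leave near-empty cells at this sample size.

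The cost is an edit to two table rows and their footnotes, one sentence in D.2, and a few minutes of questions per early exit, asked by staff whom C.14 already places with the patient. There are two small downsides. Some early exits may decline to answer, and the guesses will mix patients who had one dose with patients who had two, so the number of doses received should be recorded beside each guess.
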